4.2 Inclusion criteria

In order to be eligible to participate in this study, a subject must meet all of the following criteria:

- Idiopathic Parkinson's disease according to UK brain bank criteria.
- Presence of a clear resting tremor of at least one arm (UPDRS tremor-score \geq 2).

4.3 Exclusion criteria

A potential subject who meets any of the following criteria will be excluded from participation in this study:

- Use of beta-blockers
- Neuropsychiatric co-morbidity
- Contraindications for MRI scanning (e.g. pacemaker, implanted metal parts, deep brain stimulation, claustrophobia)
- Cardiac arrhythmias (in patient history or visible on ECG)
- contraindications for beta blockers (e.g. bradycardia, peripheral circulation disturbances, asthma or obstructive lung disease, hypotension)
- Use of medication that may interact with propranolol, e.g. other bèta-blockers, calcium antagonists, digoxine, cimetidine, hydralazine, fluvoxamine, rifampicine, barbiturates, amiodaron, flecainide, kinidine, propafenon, disopyramide, chlorpromazine, and clonidine
- Use of medication that inhibits relevant CYP enzymes that are involved in metabolizing propranolol (CYP2D6, CYP1A2, and CYP2C19): fluoxetine, paroxetine, sertraline, duloxetine, terbinafine, cinacalcet, bupropion, and ciprofloxacine
- Severe head tremor or dyskinesias
- Cognitive impairment (MMSE < 26)
- PD disease duration >10 years, severe ON/OFF medication fluctuations, or daily Levodopa-equivalent dose >1200 mg.

4.4 Sample size calculation

Formal power analyses are impossible given the highly innovative character of our approach. Our projected sample size is based on comparable fMRI experiments in PD. In these studies, a sample size of 20 patients was sufficient to find significant differences non-tremor PD patients and tremor-dominant PD patients ^{25,30}. In addition to tremor-dominant patients, we will also include non-tremor Parkinson patients, matched for age, gender, and non-tremor disease characteristics (duration, severity) with the tremor-dominant group. Here we aim to have two groups of at least 24 subjects (see section 8.5).

On March 19th 2021, data from 17 of 25 (68%) tremor-dominant patients who signed informed consent could be used for further analysis (due to 8 early drop-outs). Data from all 19 included non-tremor patients could be used for further analysis. Furthermore, ongoing data analyses from a previous study, which used the same outcome measure as done here but without a propranolol intervention, showed that 33 of 40 collected data sets contained suitable eye tracking data (83%). Accordingly, we expect that we need to include 40 tremor-

dominant patients to arrive at ± 24 individuals with complete and high-quality data (40 x $68\% \times 83\% = 23-24$ subjects). Drop-out is much less for the non-tremor group, given that there is no intervention, and only one session. In sum, this means that we will measure at maximum 40 tremor-dominant and 30 non-tremor patients. To avoid more early drop-outs in the tremor-dominant group, we will take the following measures: during screening, we will prioritize patients who have also participated in the Personalized Parkinson's Project (PPP), since a recent ECG is available for these patients. Other patients will be asked whether an ECG has been made recently, if so we will give these patients priority. We will request recent ECGs and only after an MD has approved that it meets all inclusion criteria, patients will be invited to participate. Remaining patients with no ECG available are invited to come to the institute prior to the scheduled sessions, to make an ECG and make sure they can undergo the propranolol intervention. Finally, we will be stricter in selecting suitable patients during our phone screening, and we will not invite patients with a disease duration of >10 years, considerable ON/OFF fluctuations or daily levodopa-equivalent dose of >1200 mg. In addition, shortening the protocol by leaving out the threat-of-shock task will hopefully increase quality of eye-tracking data.

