4. STUDY POPULATION

4.1 Population (base)

Patients with idiopathic PD will be included through their neurologists at the Neurology department of the Radboud University Nijmegen Medical Centre, and through ParkinsonNext (see below). Nijmegen has a very large outpatient movement disorders clinic, and based on previous studies we expect no problems in recruiting enough patients for this research.

Number of subjects:

The full experiment, including testing on two different days, will be performed in 40 idiopathic Parkinson's disease patients with a tremor-dominant phenotype, defined as a resting tremor score of \geq 2 UPDRS points for at least one arm^{3,25}. This number of subjects gives reliable and replicable (validated across multiple cohorts) tremor-related activity^{3,25,31}. Since my focus is to understand how different experimental factors modulate cerebral and clinical correlates of resting tremor, I will use a within-patients (cross-over) design.

In addition, I will perform a subset of measurements in 30 non-tremulous Parkinson patients. These patients will only receive structural MRI scanning, resting state fMRI, and task-based fMRI on one day, to localize structurally and functionally localize the locus coeruleusnoradrenaline system. This group will not receive any intervention (behavioral or pharmacological). I will compare the structural and functional integrity of the locus coeruleus between tremor-dominant and non-tremor Parkinson patients.

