8.5 Replacement of individual subjects after withdrawal

Our goal is to investigate two groups of 24 patients (tremor-dominant vs. nontremor Parkinson's disease). We count on 6 dropouts per group based on bad eye tracking data, and up to 10 additional dropouts in the tremor-dominant group due to our strict inclusion criteria (ECG and measurement of blood pressure). We will therefore include at maximum 40 tremor-dominant and 30 non-tremor patients.

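### Section 4.4 rounds its expected yield upward: 40 x 68% x 83% is 22.6, not 23-24, so at the protocol's own rates the maximum of 40 falls just short of the aim of at least 24, and section 8.5 assumes fewer early losses

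*Protocol*

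**What the plan says.** Section 4.4 of the protocol declines a formal power calculation, refers to comparable imaging studies in which 20 patients were enough, and then sets its target: "Here we aim to have two groups of at least 24 subjects". The yield is built from two observed rates. The first is retention in this trial: "On March 19th 2021, data from 17 of 25 (68%) tremor-dominant patients who signed informed consent could be used for further analysis", the other 8 being early drop-outs. The second is the share of usable eye-tracking data in a previous study without propranolol, 33 of 40, given as 83%. Multiplying 40 by both, the section prints 23-24 and describes this as enough tremor-"dominant patients to arrive at ± 24 individuals with complete and high-quality data". It concludes: "In sum, this means that we will measure at maximum 40 tremor-dominant and 30 non-tremor patients". It then lists measures against further early loss (ECG review before invitation, stricter telephone screening) and hopes that a shorter protocol will improve eye tracking. No improved rate is given for either.

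Section 8.5 reaches the same 40 by counts: a goal of 24, plus 6 losses to poor eye tracking, plus "up to 10 additional dropouts in the tremor-dominant group" because of the ECG and blood pressure criteria.

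Section 4.1 gives the number without any allowance for loss: "The full experiment, including testing on two different days, will be performed in 40 idiopathic" patients with a tremor-dominant phenotype.

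**The concern.** With no power calculation, the yield calculation in section 4.4 is what justifies the maximum of 40. The printed result does not follow from the printed factors, and the error runs in the favourable direction: the correct product lies below the target that it is meant to support. The three places that discuss the number also do not fit together. Section 4.4 uses a 32% early loss, section 8.5 allows 25% (10 of 40), and section 4.1 mentions none. A reader who wants to know how many complete tremor-dominant data sets the trial expects, and on what assumption, gets a different answer from each section.

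**Working it through.** **Inputs.** From section 4.4: maximum enrolment 40; retention 17/25 = 0.68; eye-tracking yield 33/40 = 0.825, printed as 83%; target at least 24. From section 8.5: 6 eye-tracking losses and up to 10 early losses.

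**The plan's own product.**
- Rounded rates as printed: 40 x 0.68 x 0.83 = 22.58.
- Unrounded rates: 40 x 17/25 x 33/40 = 22.44.

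The first rounds to 23, the low end of the printed range. Neither supports 24.

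**Chance of reaching 24 if the rates persist.** Treat each of the 40 as an independent success with probability p.
- p = 0.68 x 0.83 = 0.5644: P(at least 24 of 40) = 0.39.
- p = 0.68 x 0.825 = 0.561: P(at least 24 of 40) = 0.37.

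For scale, an expected yield of 24 would need 24/0.5644 = 42.5, so 43 enrolled.

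**Section 8.5 beside section 4.4.**
- 8.5: 40 - 10 - 6 = 24.
- Early losses implied by 4.4: 40 x 8/25 = 12.8, against up to 10 in 8.5.
- If the 40 includes the 25 who had already consented, 8 of the 10 allowed losses had occurred. That leaves 2 among the next 15, a retention of 13/15 = 87% against the 68% observed.

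**What retention in the remaining 15 would do.** Hold 17 of 25 fixed, retain the next 15 at an assumed rate r, then apply 0.83 for eye tracking. The expected yield is (17 + 15r) x 0.83.

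| Assumed r | Expected yield | P(at least 24) |
|---|---|---|
| 0.68 | 22.6 | 0.36 |
| 0.75 | 23.4 | 0.50 |
| 0.80 | 24.1 | 0.61 |
| 0.85 | 24.7 | 0.70 |
| 0.90 | 25.3 | 0.79 |

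The first row is slightly below 0.39 because it conditions on the 17 already observed.

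**Primary analysis.** Without the eye-tracking factor, 40 x 0.68 = 27.2.

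**The case against.** The strongest reply is that this is a rounding slip of little consequence. The product 22.58 rounds to 23, which lies inside the printed range, and the text itself writes ± 24. Most of this stands. The excess of the printed range over the product is 0.4 to 1.4 patients, which is why the point is minor. It does not remove the error, because the aim is stated as at least 24 and neither the product nor its rounding reaches that.

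A second reply is that past rates need not persist. Section 4.4 describes screening changes aimed directly at the early losses, and 87% retention among patients whose ECG has been checked in advance is plausible; 30 x 0.825 = 24.75 would then meet the target. The 10 in section 8.5 are also tied to ECG and blood pressure, whereas the 8 of 25 are all early drop-outs, so the two counts may not cover the same events. This stands too, and it rules out calling section 8.5 wrong. But the printed equation uses the unimproved rates, and no improved rate appears anywhere, so the reader cannot see which assumption supports 24.

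Four stronger readings are tempting, and the documents do not support them:

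- **That the target will more likely be missed than met.** This holds only if the past rates continue. At about 75% retention in the remaining 15, the chance is already about one half.
- **That the yield is really 18-19**, from applying the eye-tracking rate once per session. The protocol does not say whether a data set in the previous study means one session, or that complete data require usable eye tracking on both days. Squaring the rate also assumes independent failures in the same patient.
- **That the shortfall weakens the primary analysis.** Sections 8.1.1 and 10.1 describe EMG-fMRI activity in a 2 x 2 repeated-measures ANOVA and do not mention pupil data.
- **That 24 is the only size claim in the plan.** Section 4.4 also cites 20 as sufficient in comparable studies, and section 4.1 justifies 40.

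**Conclusion.** The point holds as a minor error. The printed 23-24 should be 22.6 (22.4 unrounded). At the protocol's own observed rates, the maximum of 40 tremor-dominant patients is expected to give 22-23 with complete data, one to two short of the aim, with about a 37-39% chance of reaching 24. Those probabilities assume that the rates persist and that patients and the two kinds of loss are independent.

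Sections 4.4 and 8.5 imply different early losses, about 13 and up to 10 of 40. The figure of 2 further losses among 15 rests on reading the 40 as including the 25 already consented. Section 4.1 can be read as saying that 40 patients complete both days; sections 4.4 and 8.5 show that 40 is the most that will be included, so this is a matter of clarity. For the primary EMG-fMRI analysis, about 27 of 40 would be expected at 68% retention, and nothing here puts that analysis in doubt.

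**What to change.** - **Section 4.4:** replace 23-24 with 'about 22-23 at the observed rates'. Add that reaching 24 depends on the screening and protocol-shortening measures listed there, and give the retention assumed for the patients still to be included.
- **Sections 4.4 and 8.5:** make the early-loss figures agree. Either carry the observed rate through both, or state the improved rate that leads to 10. Say whether the 10 covers all early drop-outs and whether the 40 includes those already consented.
- **Section 4.1:** say that 40 is the maximum enrolled.
- **Where the yield is discussed:** note that the eye-tracking loss concerns complete data and the pupil analyses, if that is the intention.

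The cost is a few restated figures and a slightly less favourable expected yield. No extra enrolment, design change or new analysis is needed.

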5. TREATMENT OF SUBJECTS

The research will be conducted OFF dopaminergic therapy. In all cases, the patients will arrive at least 12 hours after having taken their own dopaminergic medication ⁴⁶. Subjects they will take their own medication by the end of the experiment. There is a pharmacological intervention (propranolol 40 mg dispersed in water vs. cellulose dispersed in water, tested on different days) and a behavioral intervention (a task that allows for block-wise comparison of stress (arithmetic) and control (rest) conditions within one session). Thus, there are two different sessions on two different days. Peak plasma concentrations of propranolol are reached 1 to 2 hours after administration, and remain stable for several hours^{35,36}. Therefore, in line with previous studies⁹, I will administer propranolol (or cellulose) 105 min prior to fMRI scanning. Propranolol and cellulose will be supplied by the Radboudumc pharmacy.

In total, a patient will receive 1 tablet of Propranolol 40 mg (dispersed in water) and 1 teaspoon of cellulose (dispersed in water) on two different sessions, respectively.

5.1 Investigational product/treatment

Propranolol 40 mg tablet (dispersed in water).

5.2 Use of co-intervention (if applicable)

None.

5.3 Escape medication (if applicable)

None.

6. INVESTIGATIONAL PRODUCT

In this project, we use either propranolol 40 mg or the pharmacologically inactive cellulose dispersed in water as a placebo in order to modulate the effects induced by our stress task on tremor-related activity.

The administration of propranolol in this dose is a normal clinical treatment for treating tremor, including Parkinson's tremor^{47,48}. It has been used for many decades for treating tremor, and therefore, no unexpected serious adverse events (SUSAR's) or side effects are expected.

For our study, the approved propranolol in the Netherlands is used. We have included the summary of product characteristics (SPC) as an attachment. The certificate of analysis of the supplier of cellulose has been attached as well.

6.1 Description and justification of route of administration and dosage

We use 1 tablet of propranolol 40 mg or cellulose (as placebo) dispersed in water. The 40 mg propranolol dose has clinically relevant effects on tremor^{47,48} and has been shown to modulate the cerebral locus coeruleus-noradrenaline system in healthy subjects ⁹. The dispersion in water makes this intervention comparable to our placebo intervention (cellulose dispersed in water). Dispersion of the propranolol tablet in water allows affordable blinding of the study subjects from treatment, as the inactive cellulose dispersed in water is indistinguishable from the dispersed tablet. We justify the feasibility of the dispersion of the tablet, with the information of the KNMP kennisbank "Oralia VTGM" (https://kennisbank.knmp.nl/article/oralia_vtgm/TradeProductOral/propranolol-tablet-10-80-mg.html), that allows dispersion of propranolol tablets in water.

6.2 Dosages, dosage modifications and method of administration

All patients will receive 40 mg of Propranolol dispersed in water on one session, and they will receive cellulose dispersed in water on one other session (separate days).

6.3 Preparation and labelling of Investigational Medicinal Product

Propranolol and placebo will be labelled according to GMP-annex 13 by the Radboudumcpharmacy.

Storage of medicinal product supplies

Medication will be stored at a pharmacy cabinet at the Donders Centre for Cognitive Neuroimaging (room 0.33; technical room nr. M291.00.055). The pharmacy cabinet consists of 6 lockable drawers. The temperature of the storage area is monitored and a temperature log maintained.

See the DCCN SOP: Study-Medication-Management_SOP_DCCN_version_1.0_newtemplate.

6.4 Drug accountability

We will keep an accountability log at the Donders Centre for Cognitive Neuroimaging both for Propranolol and for the placebo (cellulose). We have attached an example drug accountability log to this study protocol.

7. NON-INVESTIGATIONAL PRODUCT

Not applicable.

8. METHODS

8.1 Study parameters/endpoints

8.1.1 Main study parameter/endpoint

Tremor-related activity and connectivity (quantified using concurrent EMG-fMRI) as a function of behaviourally induced stress and the pharmacological intervention (Propranolol).

8.1.2 Secondary study parameters/endpoints (if applicable)

Structural integrity of the locus coeruleus (quantified using neuromelanin sensitive MRI).

8.1.3 Other study parameters (if applicable)

The response of non-tremor PD symptoms (such as bradykinesia and rigidity), as well as age and gender, will be used as covariates in the analyses, despite careful matching of the two groups on these parameters. We will also quantify the effect of the intervention (Propranolol) on clinical tremor severity (rating scales).

8.2 Randomisation, blinding and treatment allocation

Not applicable.

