Study population: Two groups of idiopathic Parkinson's disease patients with either a tremor-dominant phenotype (n=40) and with a non-tremor phenotype (n=30). **Intervention (if applicable)**: The intervention only involves the tremor-dominant Parkinson group. To activate the noradrenergic system, I will use a validated and controlled stress-induction task (cognitive-coactivation: alternating blocks of mental arithmetic versus rest). Furthermore, I will test whether a pharmacological intervention (propranolol 40 mg single dose) can counteract the effects of psychological stress on the tremor circuitry. Propranolol is commonly used in clinical practice to treat tremor. The control condition will be a placebo.

Main study parameters/endpoints: (1) Tremor-related activity and connectivity (quantified using concurrent EMG-fMRI); (2) Structural integrity of the locus coeruleus (quantified using neuromelanin sensitive MRI); (3) Clinical tremor severity (quantified using tremor rating scales)

Nature and extent of the burden and risks associated with participation, benefit and group relatedness: The experimental protocol will consist of clinical measurements, and performance of a simple cognitive task in the fMRI scanner. These measurements will be performed on two mornings (duration: 4-5 hours per session). Patients will arrive in a practically defined OFF state, i.e. at least 12 hours after having taken their last dopaminergic medication. At the end of the measurement, they will resume their normal medication regime. When OFF-medication, their Parkinson symptoms may temporarily worsen, which can lead to discomfort. On one session, patients will receive a single dose of propranolol (40 mg). Propranolol is commonly used in clinical practice to treat tremor. This may sometimes lead to temporary side effects such as dizziness, bradycardia, and cold hands/feet. Patients will be extensively monitored during the measurements (blood pressure, heart rate) to avoid any health risks. In addition, our task is designed to induce psychological stress, and this may lead to some discomfort. Finally, the noise in the fMRI scanner, and lying in a small space, may lead to discomfort. If all security measures are fulfilled, then there is not risk for the patients.

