3. STUDY DESIGN

Interventions

I will manipulate the noradrenergic system using a 2x2 factorial design with factors PHARMACOLOGY (propranolol 40mg vs. placebo) and BEHAVIOR (stress induction vs. control) (Fig3). The two medication conditions (propranolol versus placebo) will be tested on two different days, to avoid carry-over effects. The two behavioural conditions (stress versus control) will be measured on the same day, in a block-wise manner, as shown in Fig 2. The order of the two medication conditions will be counter-balanced. Physiological markers of stress will be monitored throughout the scanning procedure (see below).

Pharmacological suppression of noradrenergic neurotransmission will be achieved using propranolol (40mg, oral dose). This is a non-selective β -adrenergic receptor-blocking agent that competes with β -adrenergic receptor stimulating agents at β 1- and β 2-adrenergic receptor sites. In healthy subjects, propranolol suppresses noradrenergic neurotransmission and functional connectivity within a cerebral salience network⁹. In Parkinson patients, there is mixed evidence regarding the anti-tremor effect of propranolol¹³⁻¹⁵, probably because in most cases contextual factors (stressful vs. neutral) were not taken into account³⁴. Peak plasma concentrations are reached 1 to 2 hours after administration, and remain stable for several hours^{35,36}. Therefore, in line with previous studies⁹, I will administer propranolol (or placebo) 105 min prior to fMRI scanning.

Behavioural noradrenergic stress induction will be achieved using a task that is wellvalidated task by our group, the cognitive co-activation task. This task involves alternating blocks of mental arithmetic versus rest. The dynamics of this task (rapid increases and decreases of both tremor and pupil diameter) make it possible to compare stress and rest conditions within a single fMRI session.

Measurements:

- ECG (on the first visit of the patient, prior to placebo/propranolol).

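### Section 8.2 declares randomisation, blinding and allocation not applicable, which contradicts the placebo-controlled, counter-balanced cross-over and leaves drug order and tremor rating unprotected

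*Protocol*

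**What the plan says.** The body of Protocol section 8.2, "8.2 Randomisation, blinding and treatment allocation", is a two-word entry that the topic is not applicable. It is not limited to the non-tremor group, who receive no drug.

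Other sections describe a design to which all three topics apply:

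- Summary: "The control condition will be a placebo".
- Section 3: "The two medication conditions (propranolol versus placebo) will be tested on two different days, to avoid carry-over effects", and "The order of the two medication conditions will be counter-balanced".
- Section 6.1: "Dispersion of the propranolol tablet in water allows affordable blinding of the study subjects from treatment". Only the subjects are named.
- Section 6.3: "Propranolol and placebo will be labelled according to GMP-annex 13", a task given to the hospital pharmacy.

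The Summary lists rated tremor third among the main parameters: "Clinical tremor severity (quantified using tremor rating scales)". Section 8.1.1 gives EMG-fMRI activity and connectivity as the main endpoint, and section 8.1.3 places the drug effect on rated tremor among the other parameters. Section 10.2 compares rated tremor between the two sessions by paired t-test. Section 10.1 analyses the fMRI images in a 2 x 2 repeated measures ANOVA with task and pharmacology as factors.

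**The concern.** Section 8.2 is an explicit entry, not a silence that a statistical analysis plan could fill. How order is assigned and who is blinded have to be settled before patients are dosed. Two things are left open.

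**Order.** Counter-balancing says that the two orders will occur about equally often. It does not say by what mechanism, who holds the list, or whether staff can foresee the next order. Strict alternation would satisfy section 3 and be fully predictable. The drug contrasts in section 10 name no period or sequence term, so their protection against a visit effect rests on order balance. This reaches the EMG-fMRI endpoint as well as the ratings.

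**Rating.** Blinding is described for the subject only. No section says who rates tremor, whether that person knows the session's drug, or whether the person who disperses or hands over the dose is kept apart from rating. A tremor score depends on judgement, so a rater who knows the session could shift the between-session difference with no true drug effect.

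**Working it through.** **1. The protocol's own figure.** Section 4.4 expects 40 x 68% x 83% = 22.6 complete tremor-dominant patients (22.4 with the unrounded fractions 17/25 and 33/40). It states 23-24 and aims for about 24. The small rounding difference is immaterial, and 24 is used below. The protocol gives no alpha, power, effect size or SD, so a two-sided 5% level is assumed.

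**2. How a period effect enters the drug contrast.** Let n1 patients take propranolol first and n2 take it second, with n = n1 + n2, and let π be a common shift from visit 1 to visit 2. The mean propranolol-minus-placebo difference then estimates (drug effect) + π(n2 − n1)/n.

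| Split of 24 | Share of π entering the drug contrast |
|---|---|
| 12/12 | 0 |
| 10/14 | 4/24 = 0.17 |
| 8/16 | 8/24 = 0.33 |

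**3. Chance of losing balance.** Suppose 40 patients start 20/20 and 24 remain, with loss independent of order. The number remaining in one order is hypergeometric (40, 20, 24).

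- P(10/14 or worse) = 0.33
- P(9/15 or worse) = 0.11
- P(8/16 or worse) = 0.02

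This assumes that order is fixed for all 40 at enrolment. If it were assigned only after the early drop-outs, about 40 x 0.68 = 27 would be allocated, say 14/13. Losing 3 more at random reaches 14/10 only if all 3 come from the group of 13: C(13,3)/C(27,3) = 286/2925 = 0.10. The protocol does not say when order is set, so the range is about 0.10 to 0.33.

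**4. What imbalance does to the test.** Simulated type I error of the paired t-test at n = 24, with π in SDs of the paired difference within an order group:

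| π | 12/12 | 10/14 | 8/16 |
|---|---|---|---|
| 0.3 | 4.1% | 4.7% | 6.3% |
| 0.5 | 2.9% | 4.1% | 8.3% |
| 1.0 | 0.6% | 2.4% | 12.7% |

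At 10/14 the estimate is biased but the rejection rate stays below 5%, because the unmodelled period effect also widens the spread of the differences. Inflation appears at 8/16, which is unlikely under random loss.

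**5. Rater shift, for illustration.** The documents give no figure for rater bias. With no true effect, a systematic shift of b SDs of the paired difference gives a noncentral t with n − 1 degrees of freedom and noncentrality b√n. At n = 24 the critical value is 2.069.

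| b | Noncentrality | Rejection in favour of propranolol |
|---|---|---|
| 0 | 0 | 2.5% |
| 0.2 | 0.98 | 15.4% |
| 0.3 | 1.47 | 29.1% |

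The 24 includes eye-tracking losses, which rating scales need not suffer. With 27 pairs the last two figures are 16.9% and 32.3%.

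**The case against.** The strongest reply is that section 8.2 is a careless template entry. Section 10.3 is also marked not applicable although section 8.1.3 lists other parameters, and a matched placebo suggests that real blinding was intended. That may well be so, and practice may be better than the text. It does not remove the contradiction, and nothing else in the protocol supplies the missing procedure.

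Three further points stand and limit the concern:

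- Each patient is their own control, so with balanced orders a common period effect cancels from the drug contrast. The drug-by-task interaction, central to the first aim, uses stress minus rest within a session, so an additive session-level shift drops out of it whatever the split.
- The main endpoint in section 8.1.1 is measured by instrument. Rater expectation does not directly reach it.
- The rating shifts are assumed values. They show sensitivity, not likely size.

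A reader might infer that the same staff dose and rate, or that the study is run open and unrandomised. The protocol does not say so: section 3 has the investigator administering the drug but no section names the rater, and counter-balancing does not exclude a random sequence. A reader might also infer that the trial manipulates first-visit arousal. It does not. It manipulates arithmetic against rest within a session, and propranolol against placebo between sessions; a more stressful first visit is only a possibility. A period term may also exist in an analysis plan that is not shown, so its absence here is not itself a fault.

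**Conclusion.** The contradiction is established from the text: section 8.2 cannot stand beside sections 3 and 6.1. As written, the protocol provides no random or concealed order and no blinding beyond the subject. It should be corrected before further tremor-dominant patients are dosed, because neither safeguard can be restored afterwards.

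The statistical size is conditional. For order, the chance of a 10/14 split or worse is about 0.33 if balance is set at enrolment and loss is random, passing one-sixth of any period effect into the main drug contrast. It is nearer 0.10 if order is assigned after early drop-out. The documents do not show that a period effect exists or that order was chosen selectively. For rating, the exposure is confined to the clinical tremor scores; the rise from 2.5% to about 15% or 29% holds only under assumed shifts of 0.2 or 0.3 SD at 24 pairs. Neither calculation shows that bias has occurred.

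**What to change.** Replace the entry in section 8.2 with text consistent with sections 3 and 6.1:

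- Each remaining tremor-dominant patient is randomly assigned to propranolol-placebo or placebo-propranolol in permuted blocks, from a list made and held by the pharmacy that already labels both products. Assigning order after ECG clearance would limit the imbalance caused by early drop-out.
- Both session doses are issued under code.
- The patient and the tremor rater are blind to the session's drug, and whoever prepares or gives the dispersion does not rate tremor.
- Tremor scores and EMG-fMRI data are processed under coded session labels where feasible.
- Section 8.2 states that the non-tremor group receives no drug and is not allocated.

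For patients already enrolled, report how order was set and who was blinded. Section 4.4 records 25 tremor-dominant patients with signed consent on 19 March 2021, so at most 40 − 25 = 15 of the planned maximum remained to be enrolled at that date. Reporting past practice therefore matters as much as the new rule.

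Randomisation makes order unforeseeable and gives a balanced start; it does not undo imbalance from later loss, so the final split should be reported.

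The cost is a short amendment and a pharmacy list. The small downside is keeping an existing team member's dosing and rating roles apart. If such procedures are already in use, the change is one paragraph.
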